4.Sign scoring: The three signs (conjunctival congestion, conjunctival secretion/exudation, and conjunctival edema) were scored using a 3-point scale (0 = none, 1 = mild, 2 = moderate, and 3 = severe); the researchers examined and recorded them.

5. Collection of conjunctival sac secretions: Preparation before sampling: Collect bacterial culture tubes and sterile swabs provided by the central laboratory. When sampling, fully expose the bulbar conjunctiva and fornix conjunctiva, and use a sterile swab moistened with sterile 0.9% sodium chloride solution to gently swab the surface of the conjunctival sac 4 times from the inner canthus from the inside to the outside (pay attention not to miss the inner canthus, and collect the dense secretions), avoid contact with eyelashes and eyelid margins, and use eyelid openers and other instruments when necessary. After sampling, place the specimen in a sterile transport tube, mark it, and send it to the hospital laboratory for bacterial culture. All subjects need to take secretions from both eyes for bacterial culture, and indicate the subject number and eye type.

6.Vital signs: including body temperature, heart rate, blood pressure, etc.

7.Pregnancy test: For women of childbearing age, blood/urine pregnancy test can be accepted (blood pregnancy test is the main method, if it is not met, urine pregnancy test can be selected).

8.The investigators will determine whether mydriasis is required for fundus examination. If mydriasis is required, mydriasis should be applied after secretions are collected for relevant examinations. Fundus examination or fundus photography can be accepted.

9.Medication distribution: According to the medication plan, the drugs will be distributed to the subjects. These drugs will be taken by the patients themselves or with the help of caregivers or the trial team for 7 days from D1 to D7.

10.After randomization of the subjects who meet the criteria at Visit 1, the staff of the Clinical Research Center will distribute the study drugs, and then start to instruct the subjects on the topical eye drops as soon as possible and supervise the first administration. After that, the subjects will self-administer the drugs according to the dosing regimen. On the day of Visit 2 and Visit 3, the study drugs shall not be used within 1 hour before the visit.

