3.1 Overall Design

A multi-center, randomized, parallel, positive drug-controlled study design is used. In this study, the test drug IVIEW-1201(1.0% povidone-iodine ophthalmic gel sterile solution) is selected for the test group and the positive control drug Ofloxacin Eye Drops is selected for the control group. There are a total of 120 subjects: 60 in the test group and 60 in the control group.

The subject population in this study are those aged 15 and above (inclusive) with a confirmed diagnosis of acute bacterial conjunctivitis. Subjects should complete the random allocation and initial administration of the investigational drug on the day of diagnosis.

This study will be divided into 5 visit phases, namely Visit 1 (screening/baseline period, Day 1), Visit 2 (Day 3), Visit 3 (Day 6), Visit 4/End of Treatment(EOT) (Day 8 ±1 day) and Visit 5/End of Study(EOS) (Day 14±1 day).

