3.5 Blinding

In this study, there are significant differences between the investigational drug and the positive control drug in color, taste, properties and the patient's feeling when applying the medicine. The patient can easily distinguish them, which make it very easy to break the blind. Therefore, a single-blind or blind subject design cannot be used. The excipient components of ofloxacin placebo are unknown and too difficult to obtain for a double-blind double-simulation design. Since there are marketed drugs with clear efficacy for acute bacterial conjunctivitis, there are ethical issues in using a double-blind design with a placebo of 1.0% povidone-iodine eye gel sterile solution as a control.

The study is a blinded (assessor) study design. This means that the investigators are authorized to be blinded and non-blinded. Blinded and non-blinded team members shall be relatively independent in their work, limiting non-essential communication and avoiding disclosure of blind information.

Blindness shall be established when subjects are randomized. Blindness should be maintained until the blinded data review is completed, the database is locked and the primary statistical analysis is completed; The scope of the maintenance includes the above evaluators and blinded data analysts. The unblinding will be performed after the blinded data review is completed and the database is locked, and will be performed twice through the operation of the central randomization system. The first unblinding shall be performed after the database is locked, and the unblinding area is divided into groups X and Y and sent to the blinded data analysts for statistical analysis; The second unblinding shall be performed after the completion of the primary statistical analysis, and the specific test group or positive control drug group corresponding to groups X and Y shall be determined.

4. Selection of Subject

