5.1 Investigational Drug Information

Drug Name	IVIEW-1201 (1.0% povidone-iodine ophthalmic gel sterile solution)
Specification	5g : 5mg (I2)/ bottle
Dosage Form	Eye Drops
Characteristics	It is usually a reddish brown thick liquid or gel, and after shaking it becomes a brown uniform transparent solution.
Manufacturer	Bio-Concept Laboratorie (USA)
Storage	Store in a refrigerator (2~8°C), away from light and moisture

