5.2 Control Drug Information

Drug Name	Ofloxacin eye drops (Tarivid®)
Specification	5ml:15mg /bottle
Dosage Form	Eye Drops
Characteristics	Slightly yellowish green clear solution
Manufacturer	Santen Pharmaceutical (China) Co., Ltd.
Storage	Store in sealed container at 1~30°C

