5.4 Study Drug Administration

IVIEW-1201

Shake well before use, 1 drop/eye/time in the affected eye. The drug shall be administered once at the study site on Day 1, and then at least once every 3 hours until bedtime, up to a maximum of 4 doses; The drug shall be administered 4 doses on Day 2, with an interval of at least 3 hours; The drug shall be administered 3 doses a day from Day 3 to Day 7, with an interval of at least 3 hours, with duration of administration of 7 days.

Ofloxacin Eye Drops (Tarivid®)

Shake well before use, 1 drop/eye/time in the affected eye. The drug shall be administered once at the study site on Day 1, and then at least once every 3 hours until bedtime, up to a maximum of 4 doses; The drug shall be administered 4 doses on Day 2, with an interval of at least 3 hours; The drug shall be administered 3 doses a day from Day 3 to Day 7, with an interval of at least 3 hours, with duration of administration of 7 days.

Administration Route

Sit or lie on back, tilt head back slightly, look up, place the test drug bottle mouth close to the eyelid of the affected eye, drop 1 drop, then gently close eyes and press the inner canthus of the eye with fingers for 1 to 2 minutes, then rest for about 5 minutes. If the test drug is not completely dropped into the eye during administration, add one drop. Among them, the test group needs to gently shake the drug solution before instilling it before use.

5.5 Prohibited Drugs or Treatments:

The Following Drugs or Treatments are Prohibited During the Study:

- Any eye medication other than the investigational drug;
- Nasally or bronchially inhaled steroid drugs;
- Systemic use of anti-infective drugs: various antibiotics, antiviral or antifungal drugs, etc., except non-facial local treatment;
- Eye hot or cold compress;
- All types of eye surgery and treatment, including physiotherapy
- Use of corneal contact lenses.

6. Process and Indicators

This study will be divided into 5 visit phases, namely Visit 1 (screening/baseline period, Day 1), Visit 2 (Day 3), Visit 3 (Day 6), Visit 4/EOT (Day 8 ±1 day) and Visit 5/EOS (Day 14±1 day).

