6.3 Visit 4 (D8 ± 1 day) End of Treatment

Subjects will return to the study site for a visit on Day 8±1 during the treatment period and complete the following:

- 1) Vital signs (temperature, heart rate, blood pressure)
- 2) Subjective Symptoms Score
- 3) Objective Clinical Score

- 4) Best-corrected visual acuity
- 5) Corneal fluorescein staining
- 6) Slit-lamp examination
- 7) Intraocular pressure measurement
- 8) Collection of conjunctival sac secretion
- 9) Return of investigational drug, recovery and check of diary card, and evaluation of drug compliance.
- 10) Recording of adverse events
- 11) Recording of concomitant medications

If a subject forgets to return the investigational drugs, they can be returned at Visit 5. The treatment with the investigational drug shall be terminated at the end of this visit. If the investigator determines that continued treatment is still required (IVIEW-1201 needs to be discontinued) based on the subject's symptoms and signs, the specific treatment regimen will be determined by the investigator and recorded in the eCRF. The subject will need to remain in the study until Visit 5/EOS (Day 14±1 day).

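### No drug-free interval is stated before Visit 4, a primary-endpoint visit that can fall on a dosing day, although assessor blinding is the only masking and the test drug is a brown gel-forming solution

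*Combined protocol and SAP*

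**What the plan says.** **Masking.** Section 3.5 rules out blinding the subjects because "there are significant differences between the investigational drug and the positive control drug in color, taste, properties", and relies on a blinded assessor. Its safeguard is limited communication between blinded and non-blinded staff.

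**Products.** Section 5.1 on the test drug: "It is usually a reddish brown thick liquid or gel, and after shaking it becomes a brown uniform transparent solution". Section 5.2 on the comparator: "Slightly yellowish green clear solution". Section 1.2.1 lists gellan gum among the inactive ingredients of the test drug.

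**Visit-day rule.** Flow-chart footnote 10: "On the day of Visit 2 and Visit 3, the study drugs shall not be used within 1 hour before the visit". Visits 4 and 5 are not mentioned.

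**Dosing period.** Section 5.4: "The drug shall be administered 3 doses a day from Day 3 to Day 7, with an interval of at least 3 hours". Footnote 9 has the drug taken "for 7 days from D1 to D7". The flow chart marks drug administration at Visits 1, 2 and 3 only.

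**Visit 4.** Section 6.3: "Subjects will return to the study site for a visit on Day 8±1 during the treatment period". The same section stops the study drug at the end of that visit, and footnote 12 stops the test drug once Visit 4 is complete.

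**Endpoint.** Under section 2.2.1, cure is a score of 0 for bulbar congestion and 0 for secretion/exudation at Visits 4 and 5.

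**The concern.** The colour and consistency that prevent subject blinding are placed in the eye that the blinded assessor examines. If that eye is scored soon after a dose, two things can go wrong.

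- Visible drug can tell the assessor the arm. That can move the cure score in either direction.
- Gel left in the conjunctival sac can be graded as secretion. This can happen only in the test arm, and because cure needs a secretion score of 0, one point removes a cure.

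The protocol recognises the need to separate dosing from assessment at Visits 2 and 3, yet states no separation for Visit 4, where the primary endpoint is first scored. No section covers visible residue, cleaning of the eye before scoring, or how to tell gel from secretion. Without recorded dose times, any effect could not be examined afterwards.

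**Working it through.** **Step 1. Visit days against dosing days.** Inputs: dosing Day 1 to Day 7 (footnote 9, section 5.4); visit days and windows (section 3.1); visit-day rule (footnote 10).

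| Visit | Day | Scheduled dosing day? | Stated drug-free interval |
|---|---|---|---|
| 2 | 3 | yes | 1 hour |
| 3 | 6 | yes | 1 hour |
| 4 | 7 | yes | none stated |
| 4 | 8 or 9 | no on the Day 1-7 schedule; not clearly excluded by footnote 12 and section 6.3 | none stated |
| 5 | 13-15 | no (at least 13 - 7 = 6 days after the last scheduled dosing day) | none stated |

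On the Day 1-7 schedule, 1 of the 3 days in the Visit 4 window is exposed. If footnote 12 and section 6.3 are read as dosing up to Visit 4, all 3 are. The passages cannot all be applied as written to a Visit 4 on Day 8 or 9.

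**Step 2. Size if the assessor is unmasked.** The protocol gives no cure rate, effect size or power (section 3.4 states that no sample-size calculation was done), so there is no figure to reproduce. Assumptions: 60 evaluable per arm (the planned number), equal true cure p of 60-80%, and a share s of 10-25% of one arm's uncured subjects rescored as cured.

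Shift = (1 - p) × s. The false-positive rate is the exact rejection probability of the two-sided 0.05 Pearson chi-square test, by enumerating both binomials. With no shift it is about 5% at each p.

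| p | s | Shift (points) | False-positive rate |
|---|---|---|---|
| 60% | 10% | 0.40 × 0.10 = 4 | 7.4% |
| 60% | 25% | 0.40 × 0.25 = 10 | 21.0% |
| 70% | 10% | 0.30 × 0.10 = 3 | 6.8% |
| 70% | 25% | 0.30 × 0.25 = 7.5 | 15.9% |
| 80% | 10% | 0.20 × 0.10 = 2 | 5.8% |
| 80% | 25% | 0.20 × 0.25 = 5 | 10.7% |

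The range is 2-10 points and about 6-21%.

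**Step 3. Size if residue is scored as secretion.** Let f be the share of exposed, truly cured test-arm eyes scored 1 or more for residue (assumed 5-20%) and q the share of Visit 4 assessments exposed (assumed one third, or all). The fall in the apparent test-arm cure rate is p × f × q.

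- q = 1/3: from 0.60 × 0.05 / 3 = 1 point to 0.80 × 0.20 / 3 = 5.3 points.
- q = 1: from 0.60 × 0.05 = 3 points to 0.80 × 0.20 = 16 points.

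None of the values of p, s, f or q comes from the documents.

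**The case against.** The physical premise is unproven. No section gives an ocular residence time, and section 1.2.1 describes povidone-iodine as only lightly staining and easy to clean off. The differences named in section 3.5 concern the products and what the patient notices, not how a treated eye looks to an assessor later. This stands, and it limits confidence in the size. It does not close the gap: the description is of povidone-iodine in general rather than of this gel, and no cleaning step precedes scoring.

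The path from Visits 2 and 3 to the primary endpoint is also thin. Their scores feed exploratory endpoints, and four of the seven items summed there are the subject's own ratings. They reach cure only through last-observation-carried-forward imputation (section 10.3.3), or through an assessor who learns the arm early and also scores the later visits, which nothing in the protocol prevents. That stands, so this part is secondary.

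Three stronger readings are tempting but not supported.

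- A reader might infer that the protocol permits dosing right up to Visit 4. It does not say so. It states no interval, and on the Day 1-7 schedule only a Day 7 visit is exposed.
- A reader might infer that 1 hour is too short at Visits 2 and 3. The documents show neither that nor the opposite.
- A reader might apply the 10-point shift at 70% or 80% cure and obtain a false-positive rate of 25% or 33%. That would need 0.10/0.30 = 33% or 0.10/0.20 = 50% of uncured subjects rescored, outside the 10-25% assumed.

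**Conclusion.** The point holds for Visit 4. A visit that scores the primary endpoint can fall on a scheduled dosing day with no drug-free interval stated, and the text on when treatment ends contradicts the Day 1-7 schedule. In a trial masked only through the assessor, with a test drug that looks unlike its comparator, this leaves the cure score open to unmasking in either direction and to residue being graded as secretion in the test arm.

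The size is illustrative: a shift of 2-10 points and a false-positive rate of about 6-21% under the rescoring assumptions. It could be near zero if the eye clears quickly or if few Visit 4 assessments follow a dose closely. Visits 2 and 3 are a lesser concern. The trial is exploratory, but its stated purpose is to inform Phase III, so a cheap protection of the cure score is worth having.

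**What to change.** 1. Reconcile footnotes 9, 10 and 12 with sections 5.4 and 6.3 on when dosing ends relative to Visit 4, including a Visit 4 held on Day 7. Which rule applies is for the sponsor to decide.
2. Extend footnote 10's visit-day rule to sign scoring and slit-lamp examination at Visit 4. The sponsor should set the interval and justify it as long enough for the eye to be free of visible drug.
3. Record the time of the last dose at Visits 2, 3 and 4 in the eCRF, so that cure and secretion scores can be examined by time since dose.

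Requiring all scoring to precede the day's first dose would go further, but that is a dose-timing rule and is not proposed here.

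The cost is a wording amendment, one eCRF field and some constraint on visit booking.

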1.1 Background

Acute conjunctivitis (also known as "pink eye") is the most common and contagious ocular infection in the United States, Asia and Europe and is a major cause of ocular morbidity, epidemic eye infections, loss of productivity and discomfort in patients. The primary causes are bacterial (mainly gram-positive and gram-negative), fungal, and viral (mainly adenovirus) infections^[1]. Acute bacterial conjunctivitis can occur in people of different ages, genders, regions, and social strata.

The main clinical manifestations of acute bacterial conjunctivitis are eyelid swelling, conjunctival congestion and purulent secretions on the conjunctival surface. The secretions are mucous at first and then purulent. Acute bacterial conjunctivitis usually does not cause permanent vision loss and eye structure damage, and has obvious self-limiting properties. Even without treatment, it can be cured within 10 to 14 days.

At present, acute bacterial conjunctivitis is mainly treated with topical antibiotics and broad-spectrum antibiotics. However, due to irrational use of antibiotics in clinical practice, some pathogenic bacteria develop resistance to related antibiotics. Under such circumstances, treatment with antibiotics cannot achieve the desired therapeutic effect, and the best timing for treatment will be missed, thereby indirectly increasing the medical burden of patients.

1.2 IVIEW-1201(1.0% Povidone Iodine Ophthalmic Gel Forming Sterile Solution)

1.2.1 Introduction

[figure not shown]
IVIEW-1201 is a brownish aqueous clear solution for ophthalmic administration, containing 1.0% (by weight) povidone-iodine for topical administration. After shaking, it becomes a brown, uniform, transparent solution. The active ingredient is povidone-iodine, whose chemical name is a complex of 1-vinyl-2-pyrrolidone homopolymer and iodine, and has in vitro antibacterial effects on a variety of bacteria, yeasts, fungi and human adenoviruses.

Povidone-iodine gradually releases iodine in the solvent and can release 1.4 to 2.4 ppm of free iodine in water. The powerful bactericidal mechanism of free iodine is to oxidize the active groups of pathogen protoplasmic proteins and combine with the amino groups of proteins to denature them, thereby effectively killing bacteria and other pathogens. It has the characteristics of low irritation, light yellowing, easy cleaning and no allergic reaction. It can quickly kill hundreds of bacteria including *Staphylococcus aureus*, *Escherichia coli*, *Pseudomonas aeruginosa*, *Neisseria gonorrhoeae*, *Candida albicans*, etc.

Povidone-iodine is a commercially available iodine tincture that is routinely used in ophthalmic and general surgical procedures. A single drop of PVP-I (5% to 10%) is used as an eye disinfectant before ophthalmic surgery and is approved by the FDA for this indication. Povidone-iodine has been used for the acute and chronic treatment of a variety of human indications. Povidone-iodine solutions have been shown to be effective before eye surgery (5% PVP-I)^[2,3] and before/after eye surgery (1.25% PVP-I, 2.5% PVP-I, 5% PVP-I)^[4,5]. It is also effective in treating neonatal ophthalmia (2.5% PVP-I)^[6,7] and acute ocular infection (1.25% PVP-I)^[8]. It has been clearly demonstrated in the literature that PVP-I is, in fact, tolerated and non-toxic at concentrations below 2% (w/w)^[9-11]. According to the ophthalmic literature, the active antimicrobial

drug povidone-iodine [10-14] has been shown to be well tolerated in low concentrations in animals and has low toxicity.

In a large clinical trial of 459 pediatric patients^[8], povidone-iodine solution was safe and effective in the treatment of acute conjunctivitis when administered as a single dose as well as repeated doses. At the same time, it is routinely used to prevent and treat eye infections in adults^[3-6] and infants^[7,15]. In a placebo-controlled trial of 1.25% PVP-I in 459 children for the treatment of bacterial, viral, and chlamydial conjunctivitis, no toxicity was reported on slit-lamp examination, and no subjects dropped out due to eye drop intolerance^[8]. As the PVP-I concentration decreased from 10% to 0.5%, the tolerance gradually increased and the antimicrobial efficacy also increased significantly, which is due to the balanced distribution of iodine in the aqueous solution [16]. Clinical trials of povidone-iodine (0.4% or 0.6%/dexamethasone (0.1%) eye drops in the treatment of adenoviral conjunctivitis have shown that PVP-I/dexamethasone eye drops are safe, well tolerated, and significantly promotes clinical regression and adenovirus clearance in patients with acute adenovirus conjunctivitis [17,18]. The inactive ingredients used in IVIEW-1201 (1.0% povidone-iodine ophthalmic gel sterile solution) include Gelrite® gellan gum, sodium chloride, mannitol, tromethamine, and water for injection, all of which are used in amounts below the maximum safe amount established by the FDA for use in ophthalmic preparations.

Molecular Formula: C₆H₉I₂NO

Molecular Weight: 364.951

CAS No. 25655-41-8

Figure 1 Chemical Structure of Povidone Iodine

1.2.2 Preclinical Study

1.2.2.1 Antibacterial Activity

The antimicrobial efficacy of IVIEW-1201 (PVP-I 0.6%) against *P. aeruginosa*, MRSA, and *C. parapsilosis* was tested at 15s, 30s, and 1min according to the protocol described in Journal of Clinical Microbiology, p635-639 (1982). The results showed that IVIEW-1201 (PVP-I 0.6%) could kill all tested pathogens at these time points.

1.2.2.2 Anti-viral Activity

In a cytopathic effect study with human AE549 cells, IVIEW-1201 (PVP-I 0.6%) demonstrated complete inactivation of Human Adenovirus Type 5 after 30 ± 5 minutes liquid-liquid contact at $37 \pm 2^\circ\text{C}$.

To determine whether contact with IVIEW-1201 inactivates (“kills”) virus, IVIEW-1201 was mixed directly with virus for 30 ± 5 minutes, then neutralized and the surviving virus was quantified. Neutralization controls showed that virus was effectively detected in the titer assay. Toxicity controls showed that titer plates were valid and no toxicity was observed in the 1/10 dilution of the test compound. The 70% ethanol was fully effective, and untreated virus controls were as expected. The undiluted compound IVIEW1201 (PVP-I 0.6%) was an effective virucidal, and the 1/3.2 dilution (28% after virus added) had slight virucidal activity. IVIEW1201 (PVP-I 0.6%) exhibited complete inactivation of virus.

1.2.2.3 Anti-fungal activity

IVIEW-1201 (PVP-I, 0.6%) demonstrated antimicrobial efficacy on contact with ocular isolates of Candida parapsilosis.

Following the protocol described in Journal of Clinical Microbiology, p635-639, 1982, the eradication of Pseudomona aeruginosa, MRSA and Candida Parapsilosis at 15s, 30s and 1min was measured. It showed the gel forming povidone iodine formulation IVIEW-1201 (PVP-I 0.6%) eradicated all tested pathogens at 15s, 30s and 1 minute.

